9.3	Regulatory and ethical considerations	34
9.3.1	Data safety and monitoring plan	34
9.3.2	Risk assessment	34
9.3.3	Potential benefits of trial participation	35
9.3.4	Risk-benefit assessment	35
9.4	Recruitment strategy	35
9.5	Informed consent/assent	35
9.6	Payments to subjects/families	36
10.	PUBLICATION	36
11.	REFERENCES	36
APPENDIX 1	SAMPLE TREATMENT DELIVERY MAP	43
APPENDIX 2	PEDIATRIC NEUROTOXICITY GRADING SCALE	44
APPENDIX 3	PATIENT REPORTED OUTCOME SURVEY	46

Protocol number: CHP12ST051
 Amendment number:
 Version date: April 2,, 2013

ABBREVIATIONS AND DEFINITIONS OF TERMS

Term	Definition
AKI	Acute kidney injury
AUC	Area under the plasma concentration-time curve
Block	Two consecutive treatment cycles (Cycles 1 & 2 or Cycles 3 & 4)
BMP	Basic mineral panel
BSAP	Bone-specific alkaline phosphatase
CBC	Complete blood counts
CL	Clearance
C _{max}	Peak concentration
CMP	Comprehensive mineral panel
COG	Children's Oncology Group
Course	A course of cisplatin is 60 mg/m ² daily x 2 days (total dose 120 mg/m ²); a course of doxorubicin is 37 mg/m ² daily x 2 days (total dose 75 mg/m ²); a course of HDMTX is two 12 g/m ² infusions administered 1 week apart
Cr	Creatinine
CrCL	Creatinine clearance
CR	Complete Response
Cycle	A course of cisplatin and doxorubicin followed 3 weeks later by a course of HDMTX (cycles 1-4; duration 5 weeks); OR A course of doxorubicin followed 2 weeks later by a course of HDMTX (cycles 5&6; duration 4 weeks)
EOI	End of infusion
EOT	End of therapy
FEMg	Fraction excretion of magnesium
GFR	Glomerular filtration rate
H&P	History and physical exam
HDMTX	High-dose methotrexate (12 g/m ²)
IV	Intravenous
KIM-1	Kidney Injury Molecule-1
LV	Leucovorin
MAP	Methotrexate, Adriamycin (doxorubicin), cisPlatin
Mg	Magnesium
MTX	Methotrexate
NAG	N-Acetyl-β-D-Glucosamidase
NGAL	Neutrophil Gelatinase-Associated Lipocalin
OCT2	Organic cation transporter 2
OS	Osteosarcoma
PK	Pharmacokinetics
Pre-op	Preoperatively
PPI	Proton pump inhibitor
PR	Partial Response

Protocol number: CHP12ST051

Amendment number:

Version date: April 2,, 2013

Pre-Rx	Pretreatment
PRO	Patient reported outcome
PS	Performance score (Lansky or Karnofsky)
T _{1/2}	Half-life
TDM	Treatment delivery map (roadmap)
UA	Urinalysis

PROTOCOL SYNOPSIS

STUDY TITLE	Pilot Study to Prevent the Nephrotoxicity of High-Dose Methotrexate by Prolonging the Infusion Duration and Prevent the Nephrotoxicity and Ototoxicity of Cisplatin with Pantoprazole in Children, Adolescents and Young Adults with Osteosarcoma
SPONSOR	The Gateway for Cancer Research
CLINICAL PHASE	Pilot clinical trial
PARTICIPATING SITES	The Children's Hospital of Philadelphia
STUDY RATIONALE	
Current osteosarcoma treatment regimens include drugs that are nephrotoxic and ototoxic, and the damage to kidneys and cochlear hair cells may be irreversible. Preventing these toxicities will improve the outcome in long-term survivors and may also prevent short-term treatment delays and dose reductions that can compromise the efficacy of the treatment regimen and allow for administration of higher cumulative doses of cisplatin. This pilot study evaluates pharmacologically-based approaches to:
 
 • prevent the nephrotoxic effect of high-dose methotrexate (HDMTX) by prolonging the infusion duration and thereby lowering the risk of drug precipitation in renal tubules, and • selectively block the uptake of cisplatin into renal tubular cells and cochlear hair cells by inhibiting the organic cation transporter 2 (OCT2) with the proton pump inhibitor, pantoprazole. 
These pharmacologically-based approaches to prevent nephrotoxicity and ototoxicity may also be applicable in other cancers treated with cisplatin or HDTX.

STUDY OBJECTIVES	
Primary objective
 
The primary objective is to identify more rational, pharmacologically-based drug delivery approaches to prevent nephrotoxicity from HDMTX and cisplatin and ototoxicity from cisplatin in patients with OS by:
 
 • comparing biomarkers of acute kidney injury (AKI), glomerular function and plasma and urine MTX concentrations after 12 g/m² of MTX infused over 4 and 12 hours, • comparing biomarkers of AKI, glomerular function and fractional excretion of magnesium (FEMg) after cisplatin administered with and without the OCT2 inhibitor, pantoprazole, and • comparing audiograms after cisplatin administered with and without pantoprazole. 
Secondary objectives
 
 • compare the incidence and severity (grade) of common toxicities from cisplatin/ doxorubicin administered with and without pantoprazole and from HDMTX administered as a 4 and 12 h infusion, • compare radiographic response (log ratio of tumor volumes) and histological response (percent tumor necrosis) to two cycles (10 weeks) of neoadjuvant chemotherapy for the two infusion durations of HDMTX and for cisplatin with and without pantoprazole, • correlate urinary markers of AKI and GFR estimated from serum cystatin C to standard measures of renal function (serum creatinine, urinalysis, estimated creatinine clearance, FEMg), • build a tissue microarray from biopsy, primary resection and resected metastatic tumors to evaluate the expression of proteins that are responsible for resistance

Protocol number: CHP12ST051
 Amendment number:
 Version date: April 2,, 2013

	
to the drugs in the MAP regimen and to assess expression of proteins that are targeted by new anticancer drugs under development for childhood cancers,
 
 • evaluate serum BSAP as a potential biomarker for OS, • monitor nutritional status (weight, arm circumference, skin fold thickness, pre-albumin) in patients receiving the MAP chemotherapy regimen, and • pilot an osteosarcoma-specific patient reported outcomes survey to assess the incidence and severity of tumor-related and treatment-related symptoms.
TEST ARTICLE	Pantoprazole
STUDY DESIGN	
A randomized cross-over, 2 x 2 factorial design, in which patients serve as their own control, will be used to maximize the potential to detect differences in biomarkers of AKI (NAG, NGAL, KIM-1, cystatin C) and audiograms resulting from altering the infusion duration of HDMTX and from adding pantoprazole to cisplatin.
 
Two infusion durations of HDMTX will be studied – the standard 4 h duration and more prolonged 12 h infusion duration. Leucovorin rescue will commence 24 h from the start of the infusion. The HDMTX infusions will be divided into 2 blocks (cycles 1 & 2, cycles 3 & 4), each of which include 4 HDMTX infusions. The order of infusion duration studied in each block will be randomly determined.
 
Pantoprazole will either be administered with the first two courses of cisplatin during cycles 1 & 2 or with the third and fourth courses during cycles 3 & 4, and the order will be assigned by randomization. Cisplatin is administered as a 60 mg/m² dose infused over 4 h daily x 2 d. At steady state, 7.2 mg/m² of active cisplatin is in the body, and by the end of the 4 h infusion, 88% of the total dose has been cleared. Therefore, adequate concentrations to inhibit OCT2 should be present for at least 4 h to prevent cisplatin nephrotoxicity and ototoxicity. Pantoprazole has a short half-life (1.2 h), and when administered at a dose of 1.6 mg/kg as a standard 15 min infusion, plasma pantoprazole concentration by the end of the 4 h cisplatin infusion is 1.3 mcM. By administering the same dose as a 0.3 mg/kg loading dose infused over 15 min followed by a 4 h infusion of the remaining 1.3 mg/kg, plasma pantoprazole concentration is 5.9 mcM at 4 h.
 
The primary endpoint to assess nephrotoxicity will be the AKI markers (cystatin C, KIM-1, NGAL, NAG) and fractional excretion of magnesium (FEMg). This will allow us to assess each course of HDMTX and cisplatin independently. Standard renal function tests (urinalysis, serum creatinine, estimated creatinine clearance, and FEMg) will also be monitored. Audiograms will be performed after each course of cisplatin to assess ototoxicity. Radiographic and histological response in the resected tumor specimen after neoadjuvant chemotherapy will be assessed to ensure that changes in HDMTX infusion duration and the addition of pantoprazole to cisplatin do not alter the efficacy of chemotherapy.
 
A brief survey to assess the patient’s view of disease-related and drug toxicity-related symptoms will be piloted prior to each treatment cycle, post-op and at the end of therapy, and nutritional status will be monitored over the course of therapy.
 
The use of:
 
 • sensitive, short-term biomarkers as endpoints to assess the effect of interventions, • continuous, rather than categorical, variables that are analyzed by course or cycle rather than by patient, and • a crossover design with patients serving as their own control, 
will minimize the number of subjects and time required to complete this pilot study in a limited patient population with a rare form of cancer, increase statistical power, and


Protocol number: CHP12ST051
 Amendment number:
 Version date: April 2,, 2013

	maximize the amount of data collected in this pilot study.
SUBJECT POPULATION	
Children, adolescents and young adults with previously untreated osteosarcoma
 
Inclusion Criteria
 
 • Age: <30 years of age • Diagnosis: histological diagnosis of high-grade osteosarcoma • Site: Extremity or central axis (including craniofacial) primary tumor; localized or metastatic • Prior therapy: No prior chemotherapy or radiation therapy for osteosarcoma. Subjects who develop osteosarcoma as a second cancer are eligible if they have not previously received cisplatin, doxorubicin or MTX • Kidney function: Normal serum creatinine for age and gender • Cardiac function: Shortening fraction on echocardiogram >28% • Hearing: Hearing level threshold ≤25 dB at all frequencies in both ears to be evaluable for assessment of pantoprazole's effect on cisplatin ototoxicity. Patients with hearing loss can be enrolled but will not be evaluable for ototoxicity objective. • Hematological function: Absolute neutrophil count >1,000/mcL and platelet count >100,000/mcL 
Exclusion Criteria
 
 • Receiving H₂ antagonists (cimetidine, ranitidine, famotidine, nizatidine) or proton pump inhibitors (lansoprazole, omeprazole, pantoprazole, esomeprazole, rabeprazole, dexlansoprazole) AND unable to hold the drug for 24 h prior to and 24 h after each cisplatin course on cycles 1-4. • Pregnant or breastfeeding • Unable to cooperate with research procedures
NUMBER OF SUBJECTS	24
DURATION OF SUBJECT PARTICIPATION	40 weeks
STUDY DURATION	24-36 months
STUDY PHASES	Pilot clinical trial
EFFICACY EVALUATION	Radiographic and histological response to neoadjuvant therapy, survival
PHARMACOKINETIC EVALUATION	Plasma and urine methotrexate concentrations at the end of each HDMTX infusion on cycles 1-4
SAFETY EVALUATION	
Nadir neutrophil count and duration of severe (ANC <500/mcL) neutropenia, nadir platelet count and number of platelet transfusions, hospital admissions/days for neutropenia with fever or infection, highest value for serum ALT and total bilirubin, grade 3 or 4 mucositis, treatment delays or missed chemotherapy doses to allow for recovery from toxicity, dose modifications for toxicity, and deaths attributed to chemotherapy toxicity will be monitored and collected by cycle.
 
After the first 12 patients have completed therapy, the incidence and severity of the events listed above as well as the nephrotoxicity and ototoxicity endpoints will be assessed by Cycle according to HDMTX infusion duration (4 h vs. 12 h) and according to whether or not IV pantoprazole was administered with cisplatin to ensure that the experimental dosing methods are not associated with excessive toxicity.
 
After the first 12 patients have undergone resection of their primary tumor, the radiographic response (log ratio) and histologic response (% necrosis) will be assessed according to HDMTX infusion duration (4 h vs. 12 h) during Cycles 1 & 2 and according to whether or not IV pantoprazole was administered with cisplatin during Cycles 1 & 2 to ensure that the anti-tumor effect of the MAP chemotherapy regimen is not compromised by the experimental dosing methods.

Protocol number: CHP12ST051

Amendment number:

Version date: April 2,, 2013

STATISTICAL AND ANALYTIC PLAN	
This pilot study uses a 2 x 2 factorial, randomized crossover design, which will allow patients to serve as their own control. Nephrotoxicity data will be analyzed by course for cisplatin and by dose for HDMTX, and ototoxicity data will be analyzed by cycle.
 
The primary endpoints are sensitive urinary biomarkers of AKI, standard renal function tests, and audiograms, and all endpoints will be analyzed as continuous variables.
 
Twenty-four patients will be enrolled and patients serve as their own control. Over the past 5 years, 57 newly diagnosed patients with osteosarcoma were seen and treated at CHOP. This is an average of 11.5 patients per year, indicating that we can complete accrual to this study in about two years. For each primary endpoint, separate linear mixed effects models will be constructed for comparison of cisplatin with vs. without pantoprazole and for comparison of the 4 vs. 12 h infusion durations of HDMTX.

DATA AND SAFETY MONITORING PLAN	
The research team led by the protocol PI will monitor adverse events related to the protocol therapy in real time. The progress of every patient actively receiving treatment on this study will be discussed weekly in the Solid Tumor Team Meeting. An interim analysis to assess the safety of the interventions will be performed after the first 12 patients have completed therapy.

Protocol number: CHP12ST051

Amendment number:

Version date: April 2,, 2013

SCHEDULE OF STUDY PROCEDURES

PROCEDURE	Baseline	Cycle 1	Cycle 2	Surgery	Cycle 3	Cycle 4	Cycle 5	Cycle 6	End therapy
Standard of care procedures									
Tumor biopsy	X								
H&P, PS, weight, height	X	D1, 22, 29	D1, 22, 29	Pre-op	D1, 22, 29	D1, 22, 29	D1, 15, 22	D1, 15, 22	X
CBC + Differential	X	D1 & weekly	D1 & weekly	Pre-op	D1 & weekly	D1 & weekly	D1 & weekly	D1 & weekly	X
CMP + PO ₄ , Mg	X	D1, 22	D1, 22	Pre-op	D1, 22	D1, 22	D1, 15	D1, 15	X
BMP		D29	D29		D29	D29	D22	D22	
UA w/o micro	X	D1, 22 ¹ , 29 ¹	D1, 22 ¹ , 29 ¹		D1, 22 ¹ , 29 ¹	D1, 22 ¹ , 29 ¹	D1, 15 ¹ , 22 ¹	D1, 15 ¹ , 22 ¹	X
Urine pregnancy test ²	X								
Serum creatinine ³		D22, 29	D22, 29		D22, 29	D22, 29	D15, 22	D15, 22	
Serum MTX ³		D22, 29	D22, 29		D22, 29	D22, 29	D15, 22	D15, 22	
Creatinine clearance ⁴	X				Pre-Rx		Pre-Rx		X
Echocardiogram ⁵	X				Pre-Rx		Pre-Rx		X
Audiogram	X		Pre-Rx		Pre-Rx	Pre-Rx			X
Plain X-ray of primary	X			Pre-op	Pre-Rx				X
MRI of primary	X			Pre-op	Pre-Rx ⁶				X ⁶
Chest CT scan	X			Pre-op			Pre-Rx ⁷		X
Bone or PET scan	X			Pre-op			Pre-Rx ⁷		X ⁷
Dexrazoxane		D1, 2	D1, 2		D1, 2	D1, 2	D1, 2	D1, 2	
Doxorubicin		D1, 2	D1, 2		D1, 2	D1, 2	D1, 2	D1, 2	
Cisplatin		D1, 2	D1, 2		D1, 2	D1, 2			
Pegfilgrastim		D3	D3		D3	D3	D3	D3	
HDMTX + LV rescue		D22, 29	D22, 29		D22, 29	D22, 29	D15, 22	D15, 22	
Tumor resection				X					
% Tumor necrosis				X					
Research procedures									
IV Pantoprazole		D1, 2 ⁸	D1, 2 ⁸		D1, 2 ⁸	D1, 2 ⁸			
Urinary AKI markers, Cr ⁹	X	D1, 2, 7, 22, 23, 29, 30	D1, 2, 7, 22, 23, 29, 30	Pre-op	D1, 2, 7, 22, 23, 29, 30	D1, 2, 7, 22, 23, 29, 30	D1		
Serum Cystatin C ¹⁰	X	D1, 7, 22, 29	D1, 7, 22, 29	Pre-op	D1, 7, 22, 29	D1, 7, 22, 29	D1		X
Plasma/Urinary Mg, Cr ¹¹	X	D1, 2, 7	D1, 2, 7		D1, 2, 7	D1, 2, 7	D1		X
BSAP	X			Pre-op	D1				X
Pre-albumin	X		D1	Pre-op	D1	D1	D1	D1	X
Urine MTX ¹²		EOI D22, 29	EOI D22, 29		EOI D22, 29	EOI D22, 29			
PRO survey ¹³	X		D1	Pre-op	D1	D1	D1	D1	X
Arm circum/Skin fold	X		D1	Pre-op	D1	D1	D1	D1	X

Protocol number: CHP12ST051

[figure not shown]
Amendment number:

Version date: April 2,, 2013

- ¹ Check urine pH prior to the start of HDMTX and every shift (q8h) until serum MTX <1 mcM.
- ² For females ≥ 11 years of age
- ³ At the end of the HDMTX infusion, hour 24, and daily until MTX <0.1 mcM
- ⁴ 12 or 24 hour urine collection to measure creatinine excretion plus serum creatinine
- ⁵ Repeat prior to every course of doxorubicin if SF <30% on prior cycle
- ⁶ Substitute CT scan if metal in endoprosthesis does not allow for MRI to be performed
- ⁷ Perform chest CT or bone scan only if positive for metastatic disease at baseline
- ⁸ Pantoprazole will be administered either on cycles 1 & 2 or cycles 3 & 4 based on the treatment arm to which the subject is randomized
- ⁹ Baseline; prior to cisplatin on day 1, at end of cisplatin infusion on day 2, and day 7; prior to HDMTX and 24 h after the start of the infusion on days 22/23 & 29/30 (cycles 1-4); pre-op and day 1 of cycle 5. A separate aliquot of same urine specimen saved for urine creatinine. See Section 4.0 for sample collection, processing and storage instructions.
- ¹⁰ Baseline; prior to each course of cisplatin and each dose of HDMTX (cycles 1-4) and post-treatment IF serum creatinine increases by $\geq 50\%$ compared to pretreatment value; pre-op and day 1 of cycle 5. Draw simultaneous BMP with serum cystatin C. See Section 4.1 for sample collection, processing and storage instructions
- ¹¹ Serum Mg and creatinine and spot urine for Mg and creatinine at baseline, prior to the start of the cisplatin infusions on day 1 and day 2 and on day 7 of cycles 1-4, day 1 of cycle 5, and at the end of therapy
- ¹² End of each HDMTX infusion (cycles 1-4). See Section 4.1 for sample collection, processing and storage instructions
- ¹³ Appendix 3

Protocol number: CHP12ST051
Amendment number:
Version date: April 2,, 2013

STUDY DIAGRAM

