3.1.5 Dose Modifications

Modification of the doses of cisplatin, doxorubicin, and HDMTX is required if toxicity for the drugs exceeds the thresholds listed in the Tables below on a prior treatment cycle. The percent of full protocol prescribed dose should be recorded on the TDM in the column labeled “% Dose”. If the dose is reduced by 25%, then the % Dose should be recorded as 75% (75% of the full dose).

Cisplatin:

Toxicity	Severity	Modification
Ototoxicity	>30 dB threshold at 2 kHz	Discontinue cisplatin
Nephrotoxicity	Serum creatinine >ULN for age and gender OR creatinine clearance <70 mL/min/1.73 m ²	Hold cisplatin until criterion in Section 3.1.4 is met
Neuropathy*	Grade >2 motor or sensory neuropathy	Hold cisplatin until resolved to grade ≤2

* See Appendix 2 for toxicity grading scale

Doxorubicin:

Toxicity	Severity	Modification
Myelosuppression	Planned day 22 HDMTX is delayed by >10d (cycle day >32) due to ANC <250/mcL or platelet count <50,000/mcL	Reduce doxorubicin dose by 20%
Cardiotoxicity	SF <27% (confirmed with repeat Echocardiogram 1 week later)	Hold doxorubicin until recovery to SF >28%
Mucositis	Grade 4 related to doxorubicin	Reduce doxorubicin dose by 20%

HDMTX:

Toxicity	Severity	Modification
Nephrotoxicity	Serum creatinine >ULN for age and gender OR creatinine clearance <70 mL/min/1.73 m ²	Hold HDMTX. Omit dose if renal function has not recovered after a 7-day delay
Mucositis	Grade 4 related to HDMTX	Reduce HDMTX by 50%

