5.1 Primary Endpoints

- Urinary biomarkers of acute kidney injury (KIM-1, NAG, NGAL) after each course of cisplatin (days 2 and 7) and each HDMTX infusion (24 h and day 7) on cycles 1-4 compared to baseline (pre-infusion) values
- Serum cystatin-C and creatinine prior to each course of cisplatin and each HDMTX infusion on cycles 1-4 and post-infusion cystatin-C and BMP if serum creatinine increases by $\geq 50\%$ compared to pre-infusion baseline value
- FEMg (simultaneous serum and spot urine for Mg and creatinine) prior to the start of the cisplatin infusions on days 1&2 and day 7 of cycles 1-4
- Plasma and urine MTX concentrations at the end of each HDMTX infusion on cycles 1-4
- Audiograms prior to cycles 1-4 and at the end of therapy.

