5.3 Efficacy Evaluations

- The effect of prolonging the duration of the HDMTX infusion to 12 h will be assessed by comparing urinary biomarkers of AKI and serum cystatin C and creatinine measured prior to, 24 h and 7 days after the start of each HDMTX infusion (n=8). All subjects will receive four HDMTX infusion durations of 4 h and four HDMTX infusion durations of 12 h in this crossover design, and subjects will serve as their controls. Measurement of the urine MTX concentration at the end of the infusion will be used to determine whether urinary MTX concentrations exceed the solubility limit for each HDMTX infusion.
- The effect of IV pantoprazole on cisplatin nephrotoxicity will be assessed by comparing urinary biomarkers of AKI, FEMg and serum cystatin C and creatinine measured prior to, at the end of the day 2 infusion, and on day 7 each cisplatin course (n=4). All subjects will receive cisplatin with and without pantoprazole in this crossover design, and subjects will, therefore, serve as their controls.
- The effect of IV pantoprazole on cisplatin ototoxicity will be assessed by comparing audiograms performed prior to each cisplatin infusion and at the end of therapy. All subjects will receive cisplatin with and without pantoprazole in this crossover design, and subjects will, therefore, serve as their own controls.
- Event-free and overall survival will be monitored but are not scientific objectives on this trial. An event is defined as tumor progression, relapse or death from any cause.

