6.1 Statistical Analysis Plan

6.1.1 Primary Endpoints

- **Urinary KIM-1, NAG and NGAL** will be normalized to the urinary creatinine concentration measured in the same urine specimen and expressed as ng/mg Cr. The end of infusion and 7-day post values for each biomarker will be analyzed by course for cisplatin with vs. without pantoprazole and by dose for HDMTX administered as a 4 h vs. 12 h infusion.
- **GFR** will be estimated from serum creatinine and from the cystatin C (see Section 1.3.3) prior to each course of cisplatin and each dose of HDMTX and 7-days post treatment. A decrease in the GFR will reflect toxicity from the immediately preceding course of

Protocol number: CHP12ST051
Amendment number:
Version date: April 2, 2013

cisplatin or dose of HDMTX. Change in GFR will be analyzed by course for cisplatin with vs. without pantoprazole and by dose for HDMTX administered as a 4 h vs. 12 h infusion.

- Change in **FEMg** from pre-dose 1 (day 1 of cycles 1-4) of cisplatin to pre-dose 2 (day 2 of cycles 1-4) of cisplatin and day 7 will be measured for each cycle containing cisplatin (n=4). Change in FEMg will be analyzed by course for cisplatin with vs. without pantoprazole to assess renal tubular toxicity.
- The **urinary MTX concentration** at the end of each HDMTX infusion on cycles 1-4 will be tabulated for the 4 and 12 h infusion durations and compared to the MTX solubility limit for the urine pH to determine whether the solubility limit was exceeded. End infusion urine MTX concentration will also be correlated with simultaneous serum concentration and with the severity of renal toxicity as measured by AKI biomarkers and serum creatinine and serum cystatin C.
- An **audiogram** will be performed prior to Cycles 1, 2, 3 and 4 and at the end of therapy (after cycle 6). The average hearing level (HL) threshold in dB over the frequency range of 4,000-8,000 Hz will be derived separately for each ear from each audiogram. The increase in the average HL threshold in dB from the pre-cycle 1 to pre-cycle 2, from pre-cycle 2 to pre-cycle 3, from pre-cycle 3 to pre-cycle 4, and from pre-cycle 4 to end of therapy audiograms will be derived and this increase in HL threshold will be compared for cisplatin with vs. without pantoprazole.

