		1	29	Urine Serum Urine	AKI, Cr Cystatin C MTX	Prior to D29 HDMTX infusion End of D29 HDMTX infusion	
		1	30	Urine	AKI, Cr	24 h after start of D29 HDMTX infusion	
		2	1	Urine Urine Plasma Serum Plasma - -	AKI, Cr Mg, Cr Mg, Cr Cystatin C Pre-albumin PRO Arm circ/ Skin fold	Prior to D1 cisplatin infusion	
		2	2	Urine Plasma Urine	Mg, Cr Mg, Cr AKI, Cr	Prior to D2 cisplatin infusion End of D2 cisplatin infusion	
		2	7	Urine Urine Plasma Serum	AKI, Cr Mg, Cr Mg, Cr Cystatin C		
		2	22	Urine Serum Urine	AKI, Cr Cystatin C MTX	Prior to D22 HDMTX infusion End of D22 HDMTX infusion	
		2	23	Urine	AKI, Cr	24 h after start of D22 HDMTX infusion	
		2	29	Urine Serum Urine	AKI, Cr Cystatin C MTX	Prior to D29 HDMTX infusion End of D29 HDMTX infusion	
		2	30	Urine	AKI, Cr	24 h after start of D29 HDMTX infusion	

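### The day-7 sample after high-dose methotrexate is the next pre-treatment draw, and for 6 of 8 infusions that treatment can be held or dropped for poor renal function

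*Combined protocol and SAP*

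**What the plan says.** **Endpoints.** Section 5.1 sets the urinary markers after "each HDMTX infusion (24 h and day 7) on cycles 1-4 compared to baseline (pre-infusion) values". Section 5.3 compares urinary markers, cystatin C and creatinine "measured prior to, 24 h and 7 days after the start of each HDMTX infusion (n=8". Section 6.1.1 takes the 7-day value into the analysis of the urinary markers. It estimates GFR "prior to each course of cisplatin and each dose of HDMTX and 7-days post treatment" and attributes a fall to the treatment just before it.

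**Collection.** The urinary marker row of the Schedule of Study Procedures lists "D1, 2, 7, 22, 23, 29, 30" for each of cycles 1 to 4. Day 7 there is day 7 of the cycle, which follows cisplatin. Around HDMTX, footnote 9 asks for urine "prior to HDMTX and 24 h after the start of the infusion on days 22/23 & 29/30 (cycles 1-4", and adds samples pre-op and on day 1 of cycle 5. Footnote 10 ties serum cystatin C to the time before each cisplatin course and HDMTX dose, with an extra post-treatment sample only if creatinine rises by at least 50%. The Section 4.1 table agrees. The sample correlative studies map in Appendix 1 labels the day 29 draw "Prior to D29 HDMTX infusion".

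**Treatment rules.** Section 3.1.4 delays HDMTX, and cisplatin in cycles 1 to 4, until a renal criterion is met. If renal function has not recovered after a week, doxorubicin is given without cisplatin. For HDMTX, Section 3.1.5 adds "Omit dose if renal function has not recovered after a 7-day delay".

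**The concern.** Cisplatin has its own day-7 sample on a fixed cycle day. HDMTX does not: its day-7 value is whatever is drawn before the next treatment, and most of those treatments wait for renal recovery. The timing of a primary outcome, and whether it is observed at all, then depend on the outcome. A patient whose kidneys are still impaired a week after an infusion is the one whose next dose is held. If the sample moves with the dose, it is taken after recovery. If the dose is omitted, a sample defined as preceding it has nothing to precede.

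If one infusion duration is more nephrotoxic, more of its high values are drawn late or lost, so the estimated 4 h versus 12 h difference is pulled toward zero. That matters in a pilot whose stated purpose (Section 6.2) is to find a signal strong enough to justify a larger randomized trial. The exposure is greatest for cystatin-C-based GFR, because the next pre-treatment draw is its only routine value after HDMTX.

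**Working it through.** **1. Which sample serves as day 7.** Cycles 1 to 4 last 35 days (Section 3.1.3), so day 22 + 7 = day 29, and day 29 + 7 = day 36, which is day 1 of the next cycle.

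| Infusion | Sample about 7 days later | Depends on a renal criterion? |
|---|---|---|
| Day 22, cycles 1, 2, 3, 4 | Day 29, before HDMTX | Yes (4 infusions) |
| Day 29, cycle 1 | Cycle 2 day 1, before cisplatin | Yes |
| Day 29, cycle 2 | Pre-op | No; not a chemotherapy dose |
| Day 29, cycle 3 | Cycle 4 day 1, before cisplatin | Yes |
| Day 29, cycle 4 | Cycle 5 day 1, before doxorubicin | No; the criterion covers cycles 1 to 4 only |

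This gives 6 of 8 per patient: 24 × 8 = 192 infusions, of which 24 × 6 = 144 are exposed and 48 are not. Each two-cycle block has 3 of 4 exposed, so the share is the same for both infusion durations.

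**2. The plan's own power figure.** Section 6.2 states 80% power for 0.42 SD (within-subject correlation ρ = 0) or 0.30 SD (ρ = 0.5), with 24 subjects, 4 + 4 measures and α = 0.05. For k measures per condition, the within-subject contrast has variance SD²(1 − ρ)(2/k). The test is a two-sided t test on 23 df with noncentrality δ√24 / √[(1 − ρ)(2/k)].
- ρ = 0, δ = 0.42, k = 4: 0.42 × 4.899 / 0.707 = 2.91; power 79.6%.
- ρ = 0.5, δ = 0.30, k = 4: 0.30 × 4.899 / 0.5 = 2.94; power 80.4%.

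Both figures reproduce.

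**3. Assumed loss.** The documents give no rate of held or omitted doses. I take p = 1.8%, 5% and 10%. The first two echo Section 1.3.2.1 (severe HDMTX nephrotoxicity 1.8%; delayed methotrexate excretion in 5% of courses), but neither is a hold rate. Applied to all 144 exposed samples, p gives 2.6, 7.2 and 14.4 samples.

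**4. Effect on a true 0.42 SD difference, ρ = 0.**
- *Random loss:* k = 4(1 − 0.75p), with no bias.
- *Highest values lost, one threshold for both durations:* simulation of 4,000 trials per setting, with 3 of 4 samples per condition exposed. Here p is the share of 4 h values above the threshold; the 12 h share is smaller because that mean is 0.42 SD lower.
- *Highest values lost in the 4 h condition only:* the difference shrinks by 0.75 × φ(z)/(1 − p), where φ is the standard normal density and z its upper-p point. At p = 5% this is 0.75 × 0.109, about 0.08 SD.

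| p | Random loss: power | Common threshold: apparent difference | Common threshold: power | 4 h only: power |
|---|---|---|---|---|
| 1.8% | 79.0% | 0.40 SD | 78% | 73% |
| 5% | 78.1% | 0.38 SD | 73% | 61% |
| 10% | 76.4% | 0.36 SD | 70% | 44% |

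For 0.30 SD at ρ = 0.5, the common-threshold case gives 0.29, 0.28 and 0.27 SD with power 77%, 76% and 73%.

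**5. Late rather than lost.** If a day-7 change recovers with a half-time of 4 to 10 days (assumed; not in the documents), a draw on day 14 shows 0.5^(7/4) = 0.30 to 0.5^(7/10) = 0.62 of it.

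**The case against.** A reader might infer that the primary biomarkers are measured late or not at all in patients with nephrotoxicity. The documents do not support that.
- The urinary markers are also taken 24 h after the start of every infusion already given. No later hold can remove that sample, so it stands for all 192 infusions.
- Creatinine is measured at the end of infusion, at hour 24 and daily until methotrexate is below 0.1 mcM, so delayed excretion yields more creatinine values.
- A triggered cystatin C covers creatinine rises of at least 50%.
- The renal criterion is coarse. Section 1.3.3 notes that creatinine can be normal with a GFR as low as 40, so many moderate changes would pass and be sampled on time.
- The mixed model uses all repeated measures, so one missing value does not remove a patient.
- The schedule and the correlative map also print nominal days (29 and 1). A site could reasonably draw on the calendar day even when the dose is held.

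All of this narrows the point to the day-7 component but does not remove it. The trigger has no stated sampling time or role in the model, misses a creatinine above the normal limit that rose by less than 50%, and adds no urinary markers. The nominal days conflict with the pre-dose wording of the footnotes, the Section 4.1 table and the map, and nothing says which prevails. The pre-op and cycle 5 samples are free of the renal criterion but not fixed to day 7: cycle 5 still waits for counts and mucositis, which Section 1.3.2.1 says methotrexate nephrotoxicity worsens. Section 6.1.1 has no rule for held or omitted doses.

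**Conclusion.** The point holds for the day-7 values after HDMTX, chiefly cystatin-C-based GFR and secondarily urinary KIM-1, NAG and NGAL. For 144 of 192 infusions, the sample is attached to a treatment that renal function can delay or remove. A renal hold can move it by up to about a week, to around day 14, and an omitted dose leaves it without an anchor. The likely bias is toward no difference between the infusion durations.

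The size is uncertain. The common-threshold range (apparent difference 0.40 to 0.36 SD, power about 78% to 70%) rests on assumed loss rates and on the marker itself driving the loss. That is pessimistic for urinary markers, which are not part of the hold rule; random loss is the mild end. The 4 h only column is an extreme case, not an expectation.

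Two further inferences should be avoided. The 5% figure pools 15 osteosarcoma with 45 leukemia/lymphoma patients and describes delayed excretion, so it is not a forecast of held doses. Nor do the documents support a claim that those infusions carry most of the signal. The change is worth making because it is cheap, not because the primary comparison fails without it.

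**What to change.** - In footnotes 9 and 10, the Section 4.1 table and the correlative map, schedule a urinary marker sample (with urine creatinine) and serum cystatin C with BMP at calendar day 7 (±1 day) after the start of each HDMTX infusion in cycles 1 to 4, drawn whether or not the next treatment is given.
- If the next dose is delayed, draw a separate pre-dose sample as that dose's baseline.
- Record actual sample times.
- In Section 6.1.1, name the calendar day-7 value as the outcome and the true pre-dose value as the next baseline. State how values after held or omitted doses are handled, with a sensitivity analysis. Also align the early time point: 6.1.1 names the end of infusion, whereas the schedule collects HDMTX urine at 24 h from the start.

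The cost is one extra spot urine and 3 mL of serum when a dose is delayed or omitted, in weeks when blood counts are already scheduled. Fully collected, this restores all 192 planned day-7 values and the stated power. No dosing rule changes.

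Separately, the sponsor should reconcile Sections 3.1.4 and 3.1.5. The first permits treatment if creatinine is normal or clearance exceeds 70; the second holds if creatinine is above the limit or clearance is below 70. A patient who meets only one limit is treated under one section and held under the other. By the Section 1.3.3 formula, at an assumed height of 160 cm, clearance falls below 70 once creatinine exceeds 0.413 × 160 / 70 = 0.94 mg/dL, while the listed limit for a male aged 13 to under 16 is 1.5. Which reading applies also determines how many day-7 samples are at risk.
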